6 STUDY INTERVENTION(S) AND CONCOMITANT THERAPY

6.1 STUDY INTERVENTION(S) ADMINISTERED

Please refer to the master protocol.

The maximum cycles allowed in this substudy for Cohort A are 35 cycles.

Dosing sequence:

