6.1.1 Investigational medicinal product

Investigational medicinal product (IMP) is defined as SAR444245, and pembrolizumab administered as described in [Section 4.1](#). Details of each IMP component to be administered are shown in [Table 2](#).

Preparation and administration of IMP are detailed in the pharmacy manual. Hydration is required for SAR444245 infusions. Details are provided in Section 6.1.3 of the master protocol.

Table 2 - Overview of IMP administered

Intervention name	SAR444245	Pembrolizumab
Type	See master protocol	Biologic
Dose formulation	See master protocol	Solution for infusion
Unit dose strength(s)	See master protocol	100 mg/vial
Dosage level(s)^a	24 µg/kg Q3W (or reduced to █ µg/kg █ or another lower dose level recommended by Study Board)	200 mg Q3W (for pediatric participants: 2 mg/kg, up to maximum 200 mg)
Route of administration	See master protocol	IV infusion
Use	See master protocol	Treatment of cancer (combination)
IMP or NIMP	IMP	IMP
Packaging and labeling	See master protocol	Supplied in single-dose vials containing 100 mg/4 mL pembrolizumab labelled with a multilingual booklet. 1 vial per treatment box.
Current/Former name(s) or alias(es)	NA	Keytruda

^a The total dose will be calculated based on the weight on the day of the infusion or the most recent weight assuming it was assessed in a reasonable time frame according to Investigator assessment. Study sites should make every effort to measure body weight as close to the infusion day as possible considering the variability of local process from site to site. If the infusion is prepared with the most recent weight assessed in a reasonable time frame, the participant must still be weighed on D1 of each cycle, and the weight recorded in the electronic case report form (e-CRF). Study sites should make every effort to target infusion timing to be as close to 30 minutes as possible. However, given the variability of infusion pumps from site to site, a window between -5 minutes and +10 minutes is permitted (ie, infusion time is 30 minutes -5 min/+10 min).

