6.5 DOSE MODIFICATION

6.5.1 General rules

Dose modification for SAR444245 is permitted according to the guidelines described in this section. Pembrolizumab dose reductions are not permitted. Pembrolizumab treatment may be withheld or discontinued due to toxicity.

Dose modifications different from those stated in the protocol should only be made in consultation with the Sponsor, unless required for immediate participant safety.

Cycle delay (ie, Day 1 should be delayed for all IMPs) is permitted in case of treatment-emergent adverse event (TEAE). Dose modification will be made according to the worst grade of toxicity observed within a cycle. If a participant experiences several toxicities and there are conflicting recommendations, the most conservative recommended dose adjustment should be followed. Once a dose has been decreased, intra-patient re-escalation back to the previous dose level is not permitted.

Administration of the study treatment will be discontinued in the event of a TEAE that persists despite appropriate dose modifications or any other TEAE that, in the opinion of the Investigator, warrants discontinuation.

If any of the IMP components is permanently discontinued, the other IMP component can be continued until disease progression or other criteria as detailed in Section 7.1.1 of the master protocol are met. In this case it is partial permanent discontinuation and the end of treatment (EOT) assessment will be 30 days after the date of the last administration of the remaining IMP. When all IMP components are permanently discontinued it is full permanent discontinuation.

All changes to study treatment administration must be recorded in the electronic case report form (e-CRF).

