 - Number (%) of participants with at least 1 dose reduction
 - Number (%) of participants with at least 1 dose omission
 - Number (%) of participants with at least 1 dose interrupted
 - Number (%) of participants with at least 1 dose interrupted and restarted
 - Number (%) of participants with at least 1 dose interrupted and not restarted
 - Number (%) of participants with at least 2 dose interruptions
- Dose** (number of doses started will be used as denominator)

- Number (%) of doses
- Number (%) of doses interruptions
- Number (%) of doses interruptions and restarted
- Number (%) of doses interruptions definitively stopped
- Number (%) of doses interruptions more than once
- Number (%) of doses interrupted at 1st dose, 2nd dose, subsequent doses
- Time from dose start to first interruption in minutes summarized as a continuous variable and by category.

3.6.1.3 *Pembrolizumab exposure (cohort A)*

The dose information will be assessed by the following:

- Total number of cycles started per participant
- Duration of pembrolizumab exposure (in weeks) is defined by (date of last administration of pembrolizumab + 21 – date of first administration of pembrolizumab) /7
- Actual dose (mg)
- Cumulative dose (mg): the cumulative dose is the sum of all actual doses of pembrolizumab, given from first to last administration
- Actual dose intensity (ADI in mg/week): defined as the cumulative dose divided by the duration of pembrolizumab exposure (in weeks)
- Planned dose intensity (PDI in mg /week): corresponds to the planned dose at C1D1 divided by the theoretical cycle duration expressed in weeks (i.e., 3 weeks per cycle started)
- Relative dose intensity (RDI, in %): $100 \times \frac{\text{ADI (mg/week)}}{\text{PDI (mg/week)}}$

The total number of doses, total number of cycles started, number of cycles started by participant will be summarized by category. Duration of pembrolizumab exposure, cumulative dose, ADI and RDI will be summarized quantitatively. RDI will also be summarized by category if relevant.

The following variables will be derived to describe dose modifications and dose interruptions:

- Dose omission is defined as a dose not administered at the scheduled visit.
- Dose interruption: a dose will be considered to be interrupted if the pembrolizumab administration is stopped during an infusion regardless of whether it is restarted or not.

Dose modifications and dose interruptions will be analyzed by participant as follows:

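### Pembrolizumab planned dose intensity in SAP 3.6.1.3 has a divisor that does not match its single-dose numerator, and is fixed at the Cycle 1 mg dose although pediatric doses follow current weight

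*SAP*

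**What the plan says.** SAP 3.6.1.3 (Pembrolizumab exposure, cohort A) builds RDI from four definitions:

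- Cumulative dose, in mg: "the cumulative dose is the sum of all actual doses of pembrolizumab, given from first to last administration".
- Duration of exposure, in weeks: last administration date plus 21 days, minus first administration date, divided by 7.
- Actual dose intensity (ADI), in mg/week: "defined as the cumulative dose divided by the duration of pembrolizumab exposure (in weeks".
- PDI, in mg/week: it "corresponds to the planned dose at C1D1 divided by the theoretical cycle duration expressed in weeks (i.e., 3 weeks per cycle started".

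RDI is 100 × ADI/PDI. It is summarized quantitatively, and by category if relevant. The matching PDI sentence for SAR444245 in SAP 3.6.1.2 has almost the same main clause, but its gloss is simply three weeks, and its units are µg/kg per week.

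Substudy 01, section 6.1.1, Table 2 gives the pembrolizumab dose as "200 mg Q3W (for pediatric participants: 2 mg/kg, up to maximum 200 mg". Footnote a to that table adds: "The total dose will be calculated based on the weight on the day of the infusion or the most recent weight". It also requires a weight to be recorded in the e-CRF on Day 1 of each cycle. Substudy 01, section 6.5.1 states: "Pembrolizumab dose reductions are not permitted". The master protocol (5.1, I 01) admits participants from age 12, or from 18 in France (10.7).

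**The concern.** There are two separate problems in the one definition.

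First, the PDI sentence does not fix a single computation. The main clause describes one dose over one cycle. The gloss adds *per cycle started*, words absent from the SAR444245 sentence, and the number of cycles started is itself a derived variable in the same list. A programmer could reasonably multiply by it and leave a one-dose numerator over a multi-cycle denominator.

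Second, for participants dosed by weight, ADI follows each cycle's actual mg dose while PDI stays at the C1D1 mg dose. Growth or weight loss then looks like over- or under-dosing. The SAR444245 formula avoids this because it works per kilogram.

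What is at stake is how the exposure table is read. Pembrolizumab reductions are not allowed and the SAP derives no reduction variable for it, so a reader will take an RDI below 100% to mean delayed, omitted or incomplete dosing. A participant could also fall into the wrong RDI category.

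**Working it through.** The plan gives no numerical RDI, so there is no figure to reproduce. The check applies the SAP formulas to perfect dosing: every dose given in full, every 21 days.

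**Inputs from the documents.** 200 mg every 3 weeks, or 2 mg/kg up to 200 mg for pediatric participants (Substudy 01, Table 2); 21-day cycles (Substudy 01, 1.3, footnote b); at most 35 cycles (Substudy 01, 6.1).

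**Assumption, not in the documents.** An adolescent's weight changes linearly over the course, by a total of between −10% and +20%.

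**Step 1: adults.**
- Duration for n cycles = (21(n − 1) + 21)/7 = 3n weeks.
- ADI = 200n/3n = 66.7 mg/week for every n.

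| Reading of the divisor | PDI (mg/week) | RDI, n = 1 | n = 6 | n = 10 | n = 35 |
|---|---|---|---|---|---|
| 3 weeks | 200/3 = 66.7 | 100% | 100% | 100% | 100% |
| 3 weeks × cycles started | 200/(3n) | 100% | 600% | 1000% | 3500% |

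The three-week reading also responds properly to a real shortfall. With one 14-day delay in six cycles, the duration is (119 + 21)/7 = 20 weeks, ADI = 1200/20 = 60 mg/week, and RDI = 60/66.7 = 90%.

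**Step 2: weight-dosed participants, on the favourable three-week reading.** Below the cap, each dose is 2 × current weight. With doses on time, RDI = mean dosing weight / C1D1 weight. For a linear total change c this is 1 + c/2.

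Six-cycle illustrations from 50 kg (C1D1 dose 100 mg, PDI = 100/3 = 33.3 mg/week, duration 18 weeks):
- Weight rising to 60 kg (+20%): doses 100, 104, 108, 112, 116, 120; sum 660 mg; ADI = 660/18 = 36.7; RDI = 110%.
- Weight falling to 45 kg (−10%): doses 100, 98, 96, 94, 92, 90; sum 570 mg; ADI = 570/18 = 31.7; RDI = 95%.

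The number of cycles does not alter these results: 17 and 35 cycles give the same percentages. Other totals from 50 kg are +5% → 102.5%, +10% → 105%, −5% → 97.5%. Starting at 95 kg, +10% gives 103.6% to 103.8%, because the 200 mg cap limits the rise. Constant weight, or weight staying at or above 100 kg, gives exactly 100%.

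**Step 3: planned dose taken at each cycle.** With PDI = (sum of planned doses)/(3 × cycles started), perfect dosing gives 100% in every case above. For adults PDI is 200n/3n = 66.7 mg/week, so the six-cycle course with a 14-day delay still gives 90%.

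**The case against.** The strongest reply is that the main clause governs. The theoretical duration of a cycle is three weeks, section 3.6.1.2 says so for the companion drug, and values such as 1000% would be spotted in the first dry run. That stands as far as it goes: for adults this is a defective gloss, not a demonstrated error in results. A reader might infer from the literal formula that RDI is wrong for everyone even when dosing is perfect. The documents do not support that, since the natural reading gives exactly 100% for adults, for adolescents of stable weight and for those who stay at the cap.

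A reader might also infer that the plan cannot show whether Cohort A received full-dose pembrolizumab. It can. The SAP summarizes cycle delays (3.6.1.1), pembrolizumab omissions and interruptions (3.6.1.3) and full intervention discontinuation (5.2) separately from RDI.

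It can further be said that anchoring PDI to the initial dose is a definitional choice, and that the weight paths are assumed. Both are fair. But an anchor in mg suits a flat dose. For a dose that the protocol ties to current weight, it makes the reference differ from the plan, and nothing elsewhere in either document corrects for this.

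Finally, a cycle-by-cycle reference needs a weight for cycles in which pembrolizumab was omitted, and footnote a allows preparation from an earlier weight without saying that this weight is captured. That objection is met by using the recorded Day 1 weight throughout. A small residual departure from 100% can remain where the two weights differ.

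**Conclusion.** The point holds in two limited parts. The words *per cycle started* conflict with the single-dose numerator: the literal reading gives n × 100%, the three-week reading gives a correct 100% for adults, and the text should leave no choice between them. Independently, RDI for a correctly dosed adolescent below 200 mg equals mean dosing weight over C1D1 weight. Under the assumed linear changes that is 110% at +20% and 95% at −10%, the latter large enough to be mistaken for a modest delay.

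The size depends on weight paths that the documents do not give and on the number of pediatric participants, which they do not state. Cohort A plans about 25 participants in all, and there may be few adolescents or none. RDI is a descriptive exposure measure. It does not enter CRR, ORR or the adverse event rates, and no hypothesis is tested. It is worth correcting before the tables are programmed.

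**What to change.** Replace the PDI definition in SAP 3.6.1.3 with: the sum, over cycles started, of the planned pembrolizumab dose at that cycle, divided by (3 weeks × number of cycles started). The planned dose is the protocol's own: 200 mg, or for weight-dosed participants 2 mg/kg up to 200 mg, using the recorded Day 1 weight and including cycles in which pembrolizumab was omitted. State which cycles count as started for this purpose, because SAP 3.6.1.1 counts a cycle in which any study drug was given.

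At minimum, delete *per cycle started*, and for weight-dosed participants compute PDI and ADI against the planned dose at each cycle.

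The cost is SAP wording and table programming. No new data are needed, since Day 1 weight is already required in the e-CRF.

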3.6.2 Adverse events

General common rules for adverse events

All AEs will be graded according to National cancer institute common terminology for adverse events (NCI-CTCAE version 5.0) and coded to a lower-level term (LLT), preferred term (PT), high-level term (HLT), high-level group term (HLGT), and associated primary system organ class (SOC) using the Medical Dictionary for Regulatory Activities (MedDRA) version currently in effect at Sanofi at the time of database lock. Cytokine Release Syndrome (CRS) and Immune effector cell associated neurotoxicity syndrome (ICANS) will be graded using ASTCT Consensus grading.

The AEs will be analyzed in the following 3 categories:

- Pre-treatment AEs: AEs occurring during the pre-treatment period.
- Treatment-emergent adverse events (TEAE)s: AEs that developed, worsened (according to the Investigator's opinion) or became serious during the treatment-emergent period
- Post-treatment AEs: AEs that are developed, worsened or became serious during the post-treatment period.

Similarly, the deaths will be analyzed in the pre-treatment, treatment-emergent and post-treatment periods.

The primary AE analyses will be on TEAEs. Pre-treatment and post-treatment AEs will be described separately.

An AE with incomplete or missing date/time of onset (occurrence, worsening, or becoming serious) will be classified as a TEAE unless there is definitive information to determine it is a pre-treatment or a post-treatment AE.

If the assessment of the relationship to IMP is missing for an AE, this AE will be assumed as related to IMP. Missing grade will be left as missing.

Multiple occurrences of the same event in the same participant will be counted only once in the tables within a treatment phase, using the maximum (worst) grade by treatment phase. Summaries will be provided for all grades combined and for grade ≥ 3 (including grade 5). Missing grades, if any, will be included in the "all grades" category.

The AE tables will be sorted as indicated in [Table 7](#).

Table 7 - Sorting of AE tables

AE presentation	Sorting rules
SOC, HLGT, HLT and PT	By the internationally agreed SOC order and by alphabetic order of HLGTs, HLTS and PTs.
SOC and PT	By the internationally agreed SOC order and decreasing frequency of PTs ^{a,b}
PT	By decreasing frequency of PTs ^a

a Sorting will be based on the AE incidence.

b The table of all TEAEs presented by primary SOC and PT will define the presentation order for all other tables (e.g., treatment-emergent SAE) presented by SOC and PT, unless otherwise specified.

Analysis of all adverse events

The overview of TEAE with the details below will be generated:

- Any TEAE
- Any grade ≥ 3 TEAE
- Any treatment-emergent SAE
- Treatment related TEAEs
- Treatment related TEAE of grade ≥ 3
- Serious treatment related TEAEs
- Grade 5 TEAE (any TEAE with a fatal outcome during the treatment-emergent period)
- Any TEAE leading to permanent full intervention discontinuation
- Any TEAE leading to permanent partial intervention discontinuation (discontinuation of each individual drug)

The AE summaries of **Table 8** will be generated with number (%) of participants experiencing at least one event. The analyses will be performed for all grades combined and for grades ≥ 3 . The all TEAE summary by Primary SOC and PT (and other safety summaries (e.g., SAEs, deaths), if deemed needed after TEAE evaluation) will be performed by trial impact (disruption) due to COVID-19.

Table 8 - Analyses of adverse events

Type of AE	MedDRA levels
All TEAE	Primary SOC, HLTG, HLT and PT Primary SOC and PT
TEAE related to IMP (overall) as per Investigator's judgment	Primary SOC and PT
Treatment emergent SAE	Primary SOC and PT
Treatment emergent SAE related to IMP (overall) as per Investigator's judgment	Primary SOC and PT
TEAE leading to permanent full intervention discontinuation	Primary SOC and PT
TEAE leading to permanent partial intervention discontinuation (for each individual drug)	Primary SOC and PT
TEAE leading to death (death as an outcome of the AE as reported by the Investigator in the AE page)	Primary SOC and PT
AE leading to death ^a	Primary SOC and PT
- In context of disease progression ^b	
- In context other than disease progression ^c	
Pre-treatment AE	Primary SOC and PT
Post-treatment AE	Primary SOC and PT
TEAE leading to dose interruption	Primary SOC and PT
TEAE leading to dose modification (including dose reduction, dose omission and dose delay)	Primary SOC and PT

a Death as an outcome of the AE as reported by the Investigator in the AE page

b Death within 30 days from last IMP administration and the cause of death is disease progression

c Death within 30 days from last IMP administration and for whom cause of death is not disease progression or the death occurred more than 30 days from last IMP administration and the cause of death is AE

Analysis of deaths

In addition to the analyses of deaths included in [Table 8](#) the number (%) of participants in the following categories will be provided:

- Deaths during the treatment-emergent and post-treatment periods by main reason for death
- An overview of Grade 5 AEs will be provided with the following categories:
 - Grade 5 AE (TEAE and post-treatment).
 - Fatal TEAE (regardless of date of death/period).
 - Grade 5 TEAE with a fatal outcome during the treatment-emergent period,
 - Any Grade TEAE with a fatal outcome during the post-treatment period.

- Post-treatment Grade 5 AE (excluding a TEAE that worsened to Grade 5 during the post-treatment period).

Analysis of adverse events of special interest (AESIs)

Number (%) of participants experiencing at least one adverse event of special interest will be provided, by SOC and PT. The selection will be made using the eCRF specific **AESI** tick box. Tables will be sorted as indicated in [Table 7](#).

In addition, the following analyses will be done for infusion reactions categories (i.e., infusion related reactions (IRRs), cytokine release syndrome (CRS) , flu-like symptoms (FLS) and anaphylaxis):

- Description of the infusion reactions by predefined grouping and other reported PT.
- Worst grade
- Action taken for each IMP
- Corrective treatment given (Yes, No)
- Number (%) of patients with only 1 episode, ≥ 2 , ≥ 3 , ≥ 4 and ≥ 5 episodes
- Onset of first episodes of infusion reaction (at the first infusion and subsequent infusions)
- Number (%) of patients with infusion reactions (any episodes) at the first and subsequent infusions
- Number (%) of patients with at least one infusion with two episodes of infusion reaction
- Total number of infusion reaction episodes
- Time to onset from infusion (by category: Infusion Day/1 day after infusion/ 2 to 3 days from infusion/ More than 3 days from infusion when applicable)
- Duration of infusion reaction (in days) (by category 1 day/ 2 to 3 days/ More than 3 days/not recovered)
- Number (%) of patients with infusion reactions' symptoms (as reported by investigator) by SOC and PT.

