9.4.3.5 Adverse events

All AEs will be categorized according to NCI-CTCAE V5.0 and classified by SOC and Preferred Term (PT) according to the latest available version of the Medical Dictionary for Regulatory Activities (MedDRA). Immune cell-associated neurotoxicity syndrome and CRS events will be graded using ASTCT Consensus Grading and will be summarized separately.

- Pre-treatment AEs are defined as any AEs occurring during the pre-treatment period.
- Treatment-emergent AEs are defined as AEs that develop, worsen (according to the Investigator's opinion), or become serious during the on-treatment period.
- Post-treatment AEs are defined as AEs that are reported during the post-treatment period.

For participants with multiple occurrences of the same PT, the maximum grade will be used.

The primary focus of AE reporting will be on TEAEs. Pre-treatment and post-treatment AEs will be described separately.

Treatment-emergent adverse events:

An overall summary of TEAEs will be provided. The number and percentage of participants experiencing any of the following will be provided:

- TEAEs.
- TEAEs of Grade ≥ 3 .
- Grade 5 TEAE (any TEAE with a fatal outcome during the treatment-emergent period).
- Serious TEAEs.
- Serious treatment-related TEAEs.
- TEAE leading to full intervention discontinuation.
- TEAE leading to partial intervention discontinuation (for each individual drug, if applicable).
- Treatment-related TEAEs.
- Treatment-related TEAEs of Grade ≥ 3 .

Number and percentage of participants experiencing TEAEs by primary SOC and PT will be summarized by NCI-CTCAE v 5.0 grade (all grades and Grade ≥ 3). Missing grades, if any, will be included in "all grades" category. Similar summaries will be prepared for TEAEs related to SAR444245 and those related to each individual drug (if applicable), TEAEs leading to partial intervention discontinuation (if applicable), TEAEs leading to full intervention discontinuation, TEAEs leading to dose modification, serious TEAEs, TEAEs with fatal outcome, AESIs, and AEs/SAEs occurring during the post-treatment period. In addition, the number (%) of participants with any Grade 5 AE (TEAE and post-treatment) will be summarized.

The following deaths summaries will be generated:

- Number and percentage of participants who died by study period (treatment-emergent period, post-treatment period) and reasons for death (disease progression, AE, or other reason).

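### For Cohort A the SAP plans related-TEAE tables only for the two drugs pooled, omitting the per-drug tables in the protocol without declaring the change

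*SAP*

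**What the plan says.** Master protocol Section 9.4.3.5 first describes TEAE tables by primary system organ class and preferred term, for all grades and for Grade ≥3. It then extends that format to related events: "Similar summaries will be prepared for TEAEs related to SAR444245 and those related to each individual drug (if applicable", with the closing condition attached to the individual-drug part.

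SAP Section 3.6.2, Table 8, has two relatedness rows. One is "TEAE related to IMP (overall) as per" the investigator's judgment and the other is "Treatment emergent SAE related to IMP (overall) as per Investigator's judgment". Neither is divided by drug.

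The meaning of IMP in Cohort A is fixed in Substudy 01, Section 6.1.1: "Investigational medicinal product (IMP) is defined as SAR444245, and pembrolizumab administered as described in" its design section. In Cohort C1 (Substudy 03, Section 6.1.1) the IMP is SAR444245 alone.

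SAP Section 3.6.2 also sets the rule for missing causality: "If the assessment of the relationship to IMP is missing for an AE, this AE will be assumed as related to IMP". It does not say how the rule works when there are two IMPs.

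**The concern.** Protocol Section 9.4 says the SAP will give the technical detail of the analyses summarised there. A SAP that lists fewer tables than the protocol, without comment, leaves programmers to follow the SAP, and the protocol-planned tables are then not produced.

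The loss matters in Cohort A. The secondary safety objective concerns the profile of SAR444245, alone or in combination, and its partner there brings its own immune-related toxicity (Substudy 01, Section 2.3.1.1). If the investigator attributes an event to pembrolizumab alone, it falls in the same row as one attributed to SAR444245 alone. A reader of the study report who wants to know how much of the related toxicity was laid to the experimental drug would find no planned table that answers.

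**Working it through.** No plan figure needs reproducing. The check compares the two documents output by output.

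1. **Related TEAEs by SOC and PT.** The protocol plans SAR444245-related TEAEs, plus each individual drug if applicable. For Cohort A that is two drug-specific tables (SAR444245 and pembrolizumab), each for all grades and Grade ≥3. The SAP plans no drug-specific relatedness table, only the pooled one.

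2. **Does the applicability condition excuse this?** No. As worded, it qualifies the individual-drug tables, and SAR444245 is named before it. Cohort A has two drugs, so the condition is met there in any case. The protocol attaches the same condition to partial discontinuation, and the SAP kept that output by drug: "TEAE leading to permanent partial intervention discontinuation (for each individual drug". So per-drug reporting was treated as applicable for one output and lost for another.

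3. **What pooling hides.** If causality is a yes/no judgment for each of two drugs, there are 2 × 2 = 4 patterns. One is unrelated to both. The other 4 − 1 = 3 (SAR444245 only, pembrolizumab only, both) all enter the pooled row and cannot be told apart.

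4. **Is the split restored elsewhere in the SAP?** The remaining per-drug AE outputs are partial discontinuation and, for infusion reactions only, "Action taken for each IMP". Both show what was done with each drug, not which drug was judged causal. The TEAE overview has no split by drug.

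5. **Is the change declared?** SAP Section 1 points to Section 3.9 for major changes to protocol-planned analyses. Section 3.9 lists only items from protocol amendment 1, and none concerns relatedness tables. The version history names only the estimand framework.

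6. **Missing causality.** Suppose an AE is recorded as unrelated to SAR444245 and its relationship to pembrolizumab is blank. The overall row is clear: the event counts as related. The rule does not say whether it counts for pembrolizumab only or for both drugs, so per-drug tables would need it stated.

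7. **Scope.** In Cohort C1 the pooled row and the SAR444245 row coincide, so nothing is lost. The gap concerns the 25 participants planned for Cohort A.

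**The case against.** The strongest reply is that the mismatch is narrow and that larger claims do not follow from it. Most of this stands.

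- A reader might infer that the SAP also dropped per-drug tables for serious events and a per-drug overview. It did not. Section 9.4.3.5 splits by drug only for related TEAEs; its overview entries on relatedness are unsplit, and the SAP overview matches them. The master protocol synopsis speaks only of treatment-related TEAEs.
- A reader might infer that the missing tables are what stops Cohort A from separating SAR444245 toxicity from pembrolizumab toxicity. The documents do not support that. Cohort A is a single arm without a pembrolizumab-alone control, and Substudy 01 Section 2.3.1.2 expects the drugs to act together and possibly to cause qualitatively different events. Per-drug tables would record investigator opinion.
- A reader might point to the Grade 3 AST and ALT increases in 2 of 6 participants on 24 µg/kg plus pembrolizumab (master protocol Section 4.3) as events that would be visible only in the pooled row. That section reports them as TEAEs from the first-in-human study and gives no causality. In this trial, such events would also appear in the all-TEAE tables and the graded laboratory summaries.
- A reader might call it a defect that the pooled row means different things in the two cohorts. IMP is defined within each substudy and results are presented by cohort, so this is by design.
- The safety endpoint counts TEAEs, DLTs, SAEs and laboratory abnormalities regardless of relatedness, and DLTs are already judged with reference to SAR444245. Endpoints and dose confirmation are untouched.

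None of this answers the core point: a protocol-planned table is missing from the SAP and the omission is not explained.

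**Conclusion.** The point holds as an undeclared departure from the protocol, limited to related TEAEs by SOC and PT in Cohort A. Two drug-specific tables are planned in the protocol and none in the SAP, for all 25 planned participants of that cohort. The consequence is one of reporting: the planned tables will not show which drug the investigator judged responsible. It is worth correcting before database lock because it bears on the SAR444245 safety objective and the correction is small, but it changes no endpoint.

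The conclusion rests on reading Table 8 as the list of relatedness tables to be produced. The value of the fix also depends on causality being recorded separately for each drug, which the documents do not settle. Master protocol Section 10.3.3 asks for the relationship to study intervention without naming drugs. Substudy 01 (Table 4 and Section 6.5.4.4) assumes that attribution to SAR444245 can be made.

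**What to change.** In SAP Table 8 add two rows for Cohort A, by primary SOC and PT, for all grades and Grade ≥3: TEAEs related to SAR444245, and TEAEs related to pembrolizumab, both per investigator. Keep the pooled rows. In Section 3.6.2 state that a missing relationship is imputed as related separately for each drug whose assessment is missing.

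Before this is finalised, confirm that the eCRF captures causality per drug. If it does not, declare in Section 3.9 that the protocol-planned tables will not be produced, and say why.

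Per-drug tables of related serious events and a per-drug overview are optional additions; the protocol does not commit to them. A footnote should say that the tables show investigator attribution without a pembrolizumab-alone control.

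The cost is a few extra descriptive tables and the eCRF check.
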